#### *Sensitivity Analysis based on treatment-policy strategy*

The primary analysis will be repeated based on assessments in all scheduled visits from post-baseline until Week 12, regardless of patients using rescue medication or discontinuation. The same MI method will be applied as outlined in [Section 8.1.2](#).

For each of m=25 imputed datasets, same ANCOVA model as defined in primary analysis will be carried out. Results from each of imputed datasets will be combined to generate the adjusted mean of change from baseline in platelet counts for each treatment group, as well as between-group difference (comparing each active treatment group against placebo) and the 95% CI for the difference.

#### *Sensitivity analysis based on hypothetical strategy*

The primary analysis will be repeated based on a hypothetical scenario if the rescue medication had not occurred. Specifically, applying the same rescue medication window, all assessments happened within 28 days of the use of rescue medication will be considered as missing, regardless if they are collected or not. Then all missing data will be imputed until Week 12 by Multiple Imputation (MI) method for all treatment groups, under:

- Missing at random (MAR) framework:  
Under this framework, the same MI method will be applied as outlined in [Section 8.1.2](#).
- Missing not at random (MNAR) framework:

Two imputation steps will be performed under this assumption. First step for arbitrary missing is MCMC monotone imputation which is the same as described in Section 8.1.2. The second step is control-based pattern imputation using monotone regression method with seed 2010703, in which the missing data in all active treatment groups and placebo group will be imputed based on placebo group using the neighboring-case missing values method with k=2.

If model fail to converge because the number of visit is more than number of subjects, the same approach in [Section 8.1.2](#) will be applied. When imputed value out of range (ie value <0), the value will be replaced by min value in dataset.

The same ANCOVA model defined in primary analysis will be carried out to analyze the 25 complete datasets. The SAS procedure MIANALYZE will be used to combine the results for the statistical inferences

### **8.2.3. Time to First Platelet Response**

Time to platelet response based on the non-response imputation defined in [Section 8.1.1](#) will be summarized by treatment group using Kaplan-Meier (K-M) methods with median time to platelet response (including two-sided 95% CI). K-M estimates of platelet response rates at 2-week intervals (e.g., 2-week, 4-week, etc) will be provided with corresponding two-sided 95% CIs by treatment group. The K-M curve for time to platelet response (later visit meet criteria) will be presented graphically and compared against placebo curve using log-rank test.

In addition, a proportional hazard model will be implemented as well with treatment, baseline platelet count, and prior TPO-receptor agonist use. The hazard ratios, 95% CIs and p-values will be provided to compare each active treatment group against placebo.

A listing of time to platelet response will also be provided.

### **8.2.4. Others**

Summary statistics will be provided to each endpoint listed in [Section 3.2.2.4](#) by each treatment group.

## **8.3. Exploratory Endpoints**

### **8.3.1. Peak Platelet Count**

Descriptive statistics of peak platelet count will be provided by treatment group. The difference in median peak platelet will be calculated for:

- Each active treatment group (200 mg BID, 400 mg BID) vs. placebo
- Combined active treatment groups vs. placebo
- 200 mg BID vs. 400 mg BID

Box plots will be provided to display the distribution of peak platelet count by treatment group and combined active treatment group.

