7.4 Sample Size Calculations

A minimum of 60 subjects will be enrolled in the study. Subjects will receive either 200 mg BID or 400 mg BID of SKI-O-703 or placebo in a 2:2:1 ratio.

Based on [Podolanczuk et al \(2009\)](#) at least 50% of subjects in the active treatment group will be responders (R). A sample size of 24 subjects per active treatment group and 12 subjects in the placebo group will provide approximately 82.7% power to detect a difference between response rates of 50% and 1% in the active treatment and placebo groups, respectively, at the 2-sided 5% significance level. The test statistic used in the sample size calculation was the 2-sided Fisher's Exact test using the normal approximation method.

Subjects that do not receive the study drug or do not provide at least 1 post baseline measurement will be excluded from the analysis above and replaced.

There will be no adjustment for multiple comparisons. The sample size calculation was performed using PASS 15 Power Analysis and Sample Size Software (2017). NCSS, LLC. Kaysville, Utah, USA, ncss.com/software/pass.

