7.7.5 Analyses of Exploratory Endpoints

Peak platelet will be summarized by treatment groups. The median peak platelet, and the lower and upper quartile will be provided by treatment group. The difference in median peak platelet will be calculated for:

- Each active treatment group (200 mg BID, 400 mg BID) vs. placebo
- Combined active treatment groups vs. placebo
- 200 mg BID vs. 400 mg BID

Bleeding score will be summarized by treatment group and the combined active treatment groups.

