## 3.2. Study Endpoints

### 3.2.1. Primary Endpoint

The primary endpoint, patient platelet response, is defined as platelet count  $\geq 30,000/\mu\text{L}$  and doubling the baseline (average of 2 previous counts), at any visit during the treatment period and without the use of rescue medication. Refer baseline definition to Section 4.2.

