### **3.2.3. Exploratory Endpoints**

#### *3.2.3.1. Peak Platelet Count*

- Peak platelet counts during the treatment period without use of rescue medication

For each patient, peak platelet count is patient's highest platelet count during the treatment period, without use of rescue medication.

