#### **4.4. Sample Size**

A minimum of 60 patients will be enrolled in the study. Patients will receive either 200 mg BID or 400 mg BID of SKI-O-703 or placebo in a 2:2:1 ratio.

Based on [Podolanczuk et al \(2009\)](#) at least 50% of patients in the active treatment group will be responders (R). A sample size of 24 patients per active treatment group and 12 patients in the placebo group will provide approximately 82.74% power to detect a difference between response rates of 50% and 1% in the active treatment and placebo groups, respectively, at the 2-sided 5% significance level. The test statistic used in the sample size calculation was the 2-sided Fisher's Exact test using the normal approximation method.

Patients that do not receive the study drug or do not provide at least 1 post baseline measurement will be excluded from the analysis above and replaced.

There will be no adjustment for multiple comparisons. The sample size calculation was performed using PASS 15 Power Analysis and Sample Size Software (2017). NCSS, LLC. Kaysville, Utah, USA, [ncss.com/software/pss](http://ncss.com/software/pss).

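### Peak platelet count is compared between arms only by a difference of sample medians with no measure of uncertainty, and near the planned 50% response rate that difference is unstable, most of all for 200 mg versus 400 mg.

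*SAP*

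**What the plan says.** SAP 3.2.3.1 defines the endpoint: "peak platelet count is patient's highest platelet count during the treatment period, without use of rescue medication". It draws on the same on-treatment counts as the primary response, which SAP 3.2.1 assesses "at any visit during the treatment period and without the use of rescue medication" but which also requires a count of at least 30,000/µL and a doubling of baseline.

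For comparison between arms, SAP 8.3.1 states "The difference in median peak platelet will be calculated for" four contrasts: 200 mg vs placebo, 400 mg vs placebo, combined doses vs placebo, and 200 mg vs 400 mg. Protocol 7.7.5 lists the same four. Within arms there is more. The SAP plans descriptive statistics and adds "Box plots will be provided to display the distribution of peak platelet count by treatment group and combined active treatment group". The protocol adds "The median peak platelet, and the lower and upper quartile will be provided by treatment group".

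No interval, test or model is named for the difference in medians. The general rule of two-sided 5% tests and 95% intervals (SAP 4.1 and 8, Protocol 7.7) gives no method for it.

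**The concern.** The exploratory objective in SAP 2.3 is comparison with placebo, yet this comparison would be reported as a bare number. Elsewhere the SAP attaches uncertainty to its contrasts: exact intervals for the response-rate difference (8.1.1), LS-mean differences with intervals (8.2.2), hazard ratios with intervals (8.2.3), and an ANCOVA even for SF-36, which is also exploratory (9.8). Quartiles and box plots describe each arm but do not say how precisely two arms have been distinguished.

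The choice of summary adds to this. With about half of an active arm responding, the median lies where the data are thinnest. In a Phase 2 trial of two doses, a difference of 30 x10^9/L in median peak could be read as dose-response when it is chance, and nothing in the planned output would warn the reader.

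**Working it through.** **1. Planning inputs (SAP 4.4).** 24 per active arm, 12 on placebo, and "response rates of 50% and 1% in the active treatment and placebo groups, respectively, at the 2-sided 5% significance level". The documents give no power, SD or distribution for peak count.

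**2. The plan's own figure.** Pooled normal approximation with continuity correction:
- difference = 0.50 - 0.01 = 0.49
- pooled rate = (24 x 0.50 + 12 x 0.01)/36 = 0.3367
- SE under the null = sqrt(0.3367 x 0.6633 x (1/24 + 1/12)) = 0.1671
- SE under the alternative = sqrt(0.25/24 + 0.0099/12) = 0.1060
- correction = 0.5 x (1/24 + 1/12) = 0.0625
- z = (0.49 - 0.0625 - 1.96 x 0.1671)/0.1060 = 0.943, power 82.73%

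The stated 82.74% is reproduced, so the inputs are read correctly.

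**3. Why the median jumps.** With 24 patients the median is the mean of the 12th and 13th ordered values. Suppose for now that non-responder peaks lie below responder peaks. With 11 or fewer responders both values come from non-responders; with 13 or more both come from responders; with exactly 12 there is one of each. At a true rate of 50%:
- P(exactly 12) = C(24,12)/2^24 = 2,704,156/16,777,216 = 0.161
- P(11 or fewer) = P(13 or more) = (1 - 0.161)/2 = 0.419
- two identical doses have medians on opposite sides with probability 2 x 0.419 x 0.419 = 0.35

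**4. Size of the jump.** This needs assumptions: log-normal peaks, non-responder median 18 and responder median 80 x10^9/L, log-SD about 0.35 and 0.6. Simulated 95% sampling ranges (x10^9/L):

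| Contrast | Difference of medians | Hodges-Lehmann shift | Width ratio |
|---|---|---|---|
| Dose vs dose, 24 vs 24, both 50% | -35 to +36 | -17 to +16 | 33/71 = 0.46 |
| Same, non-responder peaks overlapping 30 | -29 to +30 | -17 to +18 | 35/59 = 0.59 |
| Dose vs placebo, 24 vs 12, 50% vs 1% | 1 to 46 | 3 to 45 | 42/45 = 0.93 |

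The limits depend on how the assumed distributions are cut at 30. Discarding values on the wrong side, rather than setting them to the limit, gives about -40 to +40 against -18 to +19 for dose vs dose (37/80 = 0.46), and 0.7 to 51.2 against 2.4 to 50.6 for dose vs placebo (48.2/50.5 = 0.95). The pattern is the same.

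**5. Power, for context.** At 24 vs 12 and 50% vs 1% in the two-part model, the Wilcoxon rank-sum test has power of about 0.69. Substitutes based on medians give:
- permutation test of the median difference: 0.297 (43% of Wilcoxon)
- Mood's test with Fisher's exact p-value: 0.361 (52%)
- bootstrap 95% CI for the median difference: 0.554 (80%)
- Mood's test by chi-square: 0.641 (93%, but with type I error 0.08)

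Fisher's test on response has power of about 0.94.

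**The case against.** The strongest reply is that an exploratory endpoint in a 60-patient trial may properly stay descriptive. No decision rests on it, and spread is shown within each arm. The size of platelet change is also analysed elsewhere with intervals: change from baseline in the last two counts (SAP 8.2.2, including a sensitivity analysis that sets counts within 28 days of rescue to missing) and the consecutive-count thresholds (8.2.1). This stands, and it limits the importance of the point. It does not remove it, because none of those analyses compares the best rescue-free count between arms.

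Three stronger readings are tempting, and the documents do not support them.

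- A reader might infer that the median difference gives up about half the power of a rank analysis. The plan names no test of medians, so there is no planned power to lose. Depending on the test substituted, the shortfall is anywhere from 7% to 57%, and about one fifth for a bootstrap interval on the planned difference itself. Under a log-normal shift at 50% vs 1%, power is near 100% either way.
- A reader might take peak count as the continuous version of the primary endpoint and a rank test on it as the better test. Peak count carries no doubling-of-baseline requirement: a patient with a baseline of 20,000/µL who peaks at 38,000/µL is a non-responder above 30,000/µL. Under the model above, the rank test is weaker than the primary Fisher test (about 0.70 against 0.94).
- A reader might expect Hodges-Lehmann to cure the instability against placebo. It does not. At 50% vs 1%, about half of the pairwise differences are small and half are large, so its range is nearly as wide.

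**Conclusion.** The point holds in a limited form. All four planned contrasts of peak count lack a measure of uncertainty; this rests on the text alone. Near 50% response the chosen summary is also unstable. With separated peak distributions, two identical doses have medians on opposite sides of the responder boundary about 35% of the time. Under the assumed medians of 18 and 80 x10^9/L, their difference ranges over about -35 to +36, or up to about ±41 depending on how the distributions are cut.

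The benefit of changing is an interval on every contrast and a sampling range about half as wide for 200 mg vs 400 mg (0.46, or 0.59 if non-responder peaks overlap 30). Against placebo the estimator is only slightly steadier. All magnitudes for peak count rest on assumed distributions, and the instability shrinks if observed response is well away from 50%. The primary analysis is unaffected.

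**What to change.** In SAP 8.3.1, and for consistency Protocol 7.7.5, add for each of the four listed contrasts the Hodges-Lehmann shift in peak count, or its ratio form on the log scale, with a 95% CI. State that it is the median of all pairwise differences (or ratios) between arms, so that it is not confused with the difference of the two medians. A Wilcoxon rank-sum p-value may be added. Label all of it exploratory and unadjusted for multiplicity. Keep the medians, quartiles and box plots as description.

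Do not stratify the rank test by the randomisation factors: two binary factors give four strata, and 12 placebo patients leave about three per stratum. Do not present the rank test as stronger than the primary Fisher test.

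The cost is a few lines of text and one SAS procedure, with no new data. The downside is a few more unadjusted exploratory results.

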#### **8.4. Subgroup Analysis**

The primary endpoint will be summarized using the number (%) of patients achieving platelet response by each treatment group and the following subgroups of interest:

- Number of previous lines of therapy (0-2 vs.  $\geq 3$ )
- Response to previous treatment (non-responders vs. relapsed)
- Splenectomized patients vs. non-splenectomized patients and
- Patients with baseline platelet count  $< 15,000/\mu\text{L}$  versus patients with platelet count between  $15,000/\mu\text{L}$  to  $30,000/\mu\text{L}$ .
- Patients with prior TPO-receptor agonist use versus patients without prior TPO-receptor agonist use.
- Patients with background medication (defined in protocol Section 5.8) vs. patients without background medication.

### **9. Safety Analysis**

Continuous parameters will be summarized separately for each treatment at each scheduled visit using descriptive statistics (mean, SD, minimum, median, and maximum). Discrete parameters will be summarized separately for each treatment at each nominal time point using frequency counts and percentages.

Safety results will be summarized using the Safety set by treatment groups and the combined active treatment group, unless otherwise specified.

#### **9.1. Adverse Events**

The Medical Dictionary for Regulatory Activities (MedDRA v21.0 or later) will be used to code all adverse events (AE). All AEs, serious AEs (SAE), drug-related AEs, and drug-related SAEs will be summarized using the worst grade per National Cancer Institute (NCI) Common Terminology Criteria for Adverse Events (CTCAE) by system organ class and preferred term. The intensity of the AE will be rated using the NCI CTCAE v5.0.

An AE is defined as any untoward medical occurrence in a patient enrolled into this study regardless of its causal relationship to study drug. For the purpose of inclusion in TEAE tables, incomplete AE onset and end dates will be imputed according to [Section 4.7](#).

A treatment-emergent AE (TEAE) is defined as any event not present before exposure to study drug or any event already present that worsens in either intensity or frequency after exposure to study drug.

A treatment-related TEAE is defined as an TEAE which is considered to be related to the study drug and reported as “Possible”, “Probable” or “Definite” on the eCRF. Any TEAE with a missing relationship will be classified as a treatment-related TEAE.

A SAE is defined as an AE that

- Results in death
- Is immediately life threatening
- Requires inpatient hospitalization or prolongation of existing hospitalization
- Results in persistent or significant disability/incapacity
- Is a congenital anomaly/birth defect

An overall summary of the following AE categories will be provided by treatment group and combined active treatment group:

- Patients with any TEAE
- Patients with any treatment-related TEAE
- Patients with any serious adverse event (SAE)
- Patients with any treatment-related SAE
- Patients with any grade 3 or 4 TEAE
- Patients with any grade 3 or 4 treatment-related TEAE
- Patients with any TEAE leading to Dose Reduced or Drug Interrupted
- Patients with any TEAE leading to Drug Withdrawn
- Patients with any TEAE leading to death

Tables summarizing the incidence of TEAEs by treatment group and combined active treatment group in SOC and PT will be provided for each of the following AE categories:

- All TEAEs
- Treatment-related TEAEs
- Grade 3 or 4 TEAEs
- Grade 3 or 4 treatment-related TEAEs
- TEAEs leading to Dose Reduced or Drug Interrupted
- TEAEs leading to Drug Withdrawn
- All SAEs
- Treatment-related SAEs
- TEAEs leading to death

The number and percentage of patients who experience any TEAE categories will be summarized by treatment group and combined active treatment group for each system organ class (SOC) and preferred term (PT), with SOCs and PTs within each SOC presented in a descending order of patient incidence within combined active treatment groups, then from high dose to low dose and placebo group if applicable.

Summary table of All TEAEs by maximum toxicity grade will also be provided. If patient reports multiple occurrences of a specific AE, the patient will be counted only once on the maximum grade.

Separated listings will be prepared for All AEs, SAEs, Grade 3 or 4 TEAEs, TEAEs leading to treatment modification or discontinuation and TEAEs leading to death. The verbatim term, PT and SOC, as well as event dates and other attributes that were collected on eCRF will be included in the listing.

## **9.2. Adverse Events of Special Interest**

Adverse events of special interest (AESI) as listed below will be summarized by treatment group and combined active treatment group:

- Neutropenia
- Hepatotoxicity

The number and percentage of patients who experience any TEAE of special interest will be presented for each preferred term in a descending order of frequency within combined treatment group, then from high dose to low dose and placebo group if applicable. If patient reports multiple occurrences of an AESI, the patient will be counted only once.

A listing of AESI will be provided with verbatim term, PT and SOC presented, as well as other relevant event attributes collected on eCRF.

## **9.3. Clinical Laboratory Evaluations**

Clinical laboratory tests will be performed by both central and local laboratory. All summaries will be based on the standard international (SI) units provided by both central and local lab.

The laboratory values will be graded using CTCAE version 5.0. For hematologic and chemistry laboratory values that fall outside of the grade criteria of CTCAE version 5.0, the grade of 0 will be assigned.

Abnormal clinical laboratory values will be flagged as either high or low based on the reference ranges for each laboratory parameter.

Summary statistics of observed values, change and percent changes from baseline in numeric laboratory parameters will be provided by treatment group and combined active treatment group, and scheduled visit indicated in the schedule of events in [Appendix 15.1](#). Numeric values reported as less than (<) or greater than (>) a laboratory-defined limit will be included with the “<” or “>” signs ignored.

For relevant laboratory parameter, frequency summaries of categorical shifts from baseline grade to each post-baseline visit grade, and to the worst post-baseline grade during treatment will be provided in the graded hematology and serum chemistry parameters by treatment group and combined active treatment group.

Line plots of means and SEs will be created to display actual values and change from baseline by scheduled visit.

When there are multiple values within a post-baseline visit for a particular laboratory parameter (except platelet; refer rule of platelet to Section 8), the worst value will be taken (worst being the smallest value for criteria below a certain threshold or the largest value for criteria above a certain threshold). If a patient has a value below the threshold and above the threshold, the value furthest from the threshold will be chosen. If the distances are the same, the value with the recent date/time will be chosen.

All laboratory data will be listed, including unscheduled/repeat visits.

All laboratory data outside the normal range will be listed. For each laboratory test, individual patients with any values outside the standard reference range will have all their test results listed.

### **9.3.1. Hematology**

Hematology will be collected at visits indicated in the schedule of events ([Appendix 15.1](#)).

The following hematology assessments will be performed:

Hematocrit, hemoglobin, mean corpuscular hemoglobin, mean corpuscular hemoglobin concentration, mean corpuscular volume, platelet count, red blood cell count, total and differential (absolute and percent) leukocyte count, and erythrocyte sedimentation rate.

### **9.3.2. Serum Chemistry**

Serum chemistry will be collected at visits indicated in the schedule of events ([Appendix 15.1](#)).

The following serum chemistry assessments will be performed:

Alanine aminotransferase, albumin, alkaline phosphatase, AST, bilirubin (total and direct if clinically indicated), blood urea nitrogen, calcium, creatinine, gamma-glutamyltransferase, glucose, lactate dehydrogenase, serum electrolytes (sodium, potassium, chlorine, magnesium, phosphate) and total protein.

